4.3. Randomization, Stratification, and Blinding

After completing the screening assessments, participants will be randomly assigned at the Day 1 visit to receive one of the following (1:1 randomization):

- ADG20 300 mg administered IM
- Placebo administered IM

Randomization will be assigned in a blinded manner using IRT, in accordance with a pre-generated randomization schedule, generated by SAS software Version 9.4 or later (SAS Institute Inc, Cary, North Carolina), linking sequential participant randomization numbers to treatment codes. Randomization will be stratified by age (age 12 to 17, 18 to 65, and >65 years) and country; it will also use an appropriate block size, known only by the statistician. A participant is considered randomized when a randomization transaction has been recorded in the IRT.

The main goal of the stratification by country is to promote the balance in important prognostic and predictive factors across the two treatment groups within a country to help increase comparability of the two treatments rather than incorporating stratification into the analyses to increase the precision of the estimates. Therefore, the country term will not be included as strata in the statistical models.

A participant's treatment assignment will not be unblinded to site staff, sponsor personnel (or designee) working directly with the site staff, or participants until the end of the study (Month 14 of Phase 3) unless medical treatment of the participant depends on knowing the study treatment the participant received. If the blind needs to be broken due to a medical emergency, the investigator may unblind an individual participant's treatment allocation.

Details of blinding are provided in Section 5.5 of the protocol and in the PPD Work Process Flow for Maintaining the Blind.

4.4. Multiplicity Adjustments

To control the overall type I error rate at .05 (2-sided), a hierarchical testing procedure will be used, such that testing for the key secondary analyses difference will proceed only if the treatment difference is statistically significant in the primary analysis.

Analyses of the other secondary and exploratory endpoints will be conducted to support the findings of the primary and key secondary efficacy analyses without accounting for multiple comparisons. Nominal p-values and 95% CIs will be computed for these secondary and exploratory efficacy analyses when applicable.

4.5. Analysis Sets

4.5.1. Screen Failures

Screen failures are defined as participants who consent to participate in the study but who are not subsequently randomly assigned to treatment. Minimal information collected includes date of informed consent (and assent, where applicable for adolescents), reason for screen failure, and AE information. Individuals who do not meet the criteria for participation in this study (screen failure) may be rescreened. A participant is considered enrolled once the participant has been randomized.

4.5.2. Full Analysis Set

The Full Analysis Set (FAS) will include all randomized participants regardless of whether the participant received study drug. Participants will be analyzed based on the treatment they are randomized to, irrespective of which treatment was actually received.

4.5.3. SARS-CoV-2 Variant Specific Analysis Sets

WGS will be used to determine a participant's SARS-CoV-2 infecting variant (Delta, Omicron, and others) based on the NP or saliva sample collected at baseline; if the baseline sample is missing, the available post-baseline NP or saliva sample will be used. Any participants with a missing WGS result will be classified as suspected non-Omicron or Omicron variant by comparing their randomization date with the date of the first WGS-confirmed Omicron participant enrolled from the same country. If there is no WGS-confirmed Omicron participant enrolled from the same country in the study, the date of emergence of Omicron in the country, based on publicly available epidemiology data will be used (see [Appendix E](#)). A final clinical and virological review (with adjudication as needed) may be performed.

Modified Full Analysis Set with Non-Omicron SARS-CoV-2 Variant (mFAS-non-Omicron): will include all randomized participants with COVID-19 due to WGS-confirmed or suspected non-Omicron SARS-CoV-2 variants, regardless of whether the participant received study drug. The mFAS-non-Omicron is the primary efficacy population.

Modified Full Analysis Set with Omicron SARS-CoV-2 Variant (mFAS-Omicron): will include all randomized participants with COVID-19 due to WGS-confirmed or suspected Omicron SARS-CoV-2 variant, regardless of whether the participant received study drug.

4.5.4. Modified Full Analysis Set-PCR

Modified Full Analysis Set-PCR (mFAS-PCR): will include all randomized participants with a positive baseline quantitative SARS-CoV-2 RT-PCR based on either an NP swab or saliva sample and who received study drug. Participants will be analyzed based on the treatment they are randomized to, irrespective of what treatment was actually received.

Two sub-populations of the mFAS-PCR will be defined:

- **mFAS-NP:** will utilize the baseline NP swab to determine a positive SARS-CoV-2 PCR
- **mFAS-S:** will utilize the baseline saliva sample to determine a positive SARS-CoV-2 PCR.

mFAS-non-Omicron-PCR: is the subset of the mFAS-non-Omicron with a positive baseline SARS-CoV-2 RT-PCR. The subpopulations mFAS-non-Omicron-NP and mFAS-non-Omicron-S based on sample type used to determine a positive SARS-CoV-2 PCR (as defined above) will also be analyzed.

mFAS-Omicron-PCR: is the subset of the mFAS-Omicron with a positive baseline SARS-CoV-2 RT-PCR. The subpopulations mFAS-Omicron-NP and mFAS-Omicron-S based on sample type used to determine a positive SARS-CoV-2 PCR (as defined above) will also be analyzed.

4.5.5. Per-Protocol Set

The PPS includes all participants in the mFAS-non-Omicron who had no significant protocol deviations (as defined in Section 5.1.2) that affect the efficacy assessments, received the full dose of study drug as randomized, and for whom the primary efficacy endpoint was assessed (ie, it is known whether or not the participant had a COVID-19-related hospitalization or all-cause death through Day 29). Protocol deviations are tracked in the PPD CTMS. The Sponsor will perform blinded review of all significant protocol deviations prior to database lock to determine if the deviation excludes the participant from the PPS.

4.5.6. Safety Set

The Safety Set will include all participants who received any amount of study drug. All safety analyses will be conducted in this analysis set. Participants will be analyzed based on the study drug actually received.

4.5.7. Immunogenicity Set

The Immunogenicity Set includes all participants who received any study drug, had a valid immunogenicity test result before the dose of study drug, and had at least 1 valid result after the dose of study drug.

4.5.8. PK Analysis Set

The PK Analysis Set includes all participants in the Safety Set who had at least one measurable ADG20 concentration post-administration of study drug. Where participants experience issues that may affect exposure to study drug (eg, dosing errors, etc), data will be reviewed by the study pharmacokineticist and evaluated for exclusion from the PK analysis set on a case-by-case basis. All participants excluded from the PK analysis set will be documented in the data listings.

5. STATISTICAL ANALYSES

5.1. Participant Disposition

5.1.1. Disposition

Participant disposition will be summarized for all screened participants, in the following categories:

- Number of screened participants and number and percentage (based on total screened) of screen failure participants
- Number and percentage of participants randomized
- Number and percentage (based on total randomized) of participants randomized and not treated

Reason for screen failure will also be summarized by number and percentage of participants with percentage based on the number of Screen Failure participants. The possible reasons for screen failure are:

- Failure to meet randomization criteria
- Physician decision
- Withdrawal by participant/guardian/LAR
- Other

The number and percentage (based on total number in the FAS) of participants randomized will be presented for all analysis sets.

The following summary will be presented in the FAS, the mFAS-non-Omicron, and the mFAS-Omicron analysis sets:

- The number and percentage of participants completing and not completing dosing
- The reasons for not completing dosing (ie, reasons for treatment discontinuation) as recorded in the eCRF and chosen from the following list:
 - Adverse Event
 - Investigator's discretion
 - Protocol Deviation

- Withdrawal by parent/guardian
- Withdrawal by participant
- Other
- The number and percentage of participants who completed the study through Days 29, 60, and 90 and through Months 6, 11, and 14
- The number and percentage of participants who discontinued from the study (early termination) prior to Day 29, prior to Month 6, and prior to Month 14.
- The reasons for early discontinuation as recorded in the eCRF and selected from the following list:
 - Death
 - Participant's request
 - Withdrawal of consent
 - Lost to Follow-up
 - Other

Participant disposition data will also be presented in listings, including a listing of participants by analysis set, and a listing of participants excluded from the Per Protocol Set.

5.1.2. Protocol Deviations

All protocol deviations will be assessed according to a study deviation rules document that indicates whether each deviation is significant or non-significant. Significant deviations are defined as protocol deviations that affect the primary efficacy and safety assessments, the safety or mental integrity of a participant, or the scientific value of the study. Non-significant deviations are defined as protocol deviations that are identified but do not impact the endpoints, safety or mental integrity of a participant, or the scientific value of the trial project. Rules for defining significant protocol deviations will be developed, documented in the study deviation rules document, and finalized in a blinded manner before database lock.

The number and percentages of participants with at least one protocol deviation, one significant deviation and one non-significant deviation will be presented in the FAS by treatment group and overall. Significant protocol deviations will also be summarized by deviation type and subtype. A table will be provided for Day 29 and Month 14. A listing of all protocol deviations will be provided for all FAS participants.

5.2. Demographics and Clinical Characteristics

The following summary will be presented in the FAS, the mFAS-non-Omicron, and the mFAS-Omicron analysis sets.

5.2.1. Demographics

Descriptive statistics will be calculated for the following continuous demographic and baseline characteristics: age (years), weight (kg), height (cm), BMI (kg/m^2). BMI is calculated as (body weight in kilograms) / (height in meters)². The number and percentage of participants will be provided for the following categorical variables: age group (age 12 to 17, 18 to 65, >65 , ≥ 50 , >55 , >70 , and >75 years), country, sex (male, female), race (White, Black or African American, Asian, American Indian or Alaska Native, Native Hawaiian or Other Pacific Islander, Other, and Multiple [if more than one race category is selected]), ethnicity (Hispanic or Latino, Not Hispanic or Latino), and BMI subgroups (for adults ≥ 25 , ≥ 30 , $\geq 40 \text{ kg}/\text{m}^2$; for adolescents $\geq 85^{\text{th}}$ percentile for age and sex based on CDC growth charts for adolescents) ([CDC 2001](#)).

Participant demographics will be presented in a listing.

5.2.2. Clinical Characteristics

Risk factors for COVID-19 progression: The number and percentage of participants with each of the protocol-defined baseline risk factors for COVID-19 progression will be summarized separately for adults and adolescents. The number of participants with ≥ 1 , ≥ 2 and ≥ 3 risk factors present at baseline will be summarized. Given differences in the definition of high risk for COVID-19 progression in this study and other mAbs that have received FDA EUA, a summary of the risk factors in the definition in the FDA EUA fact sheets may also be presented.

Duration of COVID-19 symptoms: The duration of symptom onset to randomization (defined as the time from date of onset of self-reported symptoms to the date of randomization) will be summarized with descriptive statistics and the number and percentage of participants with duration of symptoms of 0-3 days, 4-5 days, and >5 days. The duration of symptom onset to study drug administration will be summarized similarly.

COVID-19 symptoms: COVID-19 symptoms and their severity at baseline based on the symptom diary on Day 1 will be presented. The number and percentage of participants with at least 1 severe symptom, at least 1 moderate symptom and no severe symptoms, and those with only mild symptoms on Day 1 will be summarized.

COVID-19 severity: In addition, investigator-assessed COVID-19 severity (SARS-CoV-2 infection without symptoms, mild, moderate, severe, critical) will be presented as will a programmatic determination of baseline severity based on parameters collected in the eCRF and patient diary outlined in [Table 3](#). The programmatic derived COVID-19 severity will be performed at baseline and for the maximum severity through Day 29.

Table 3: Programmatic Determination of COVID-19 Severity

Protocol Defined COVID-19 Severity	Programmatic Determination
Critical COVID-19, as defined in Section 2.2.2 of the protocol	Positive local RT-PCR test at baseline, and one of the following: 
Any concomitant procedure entry of: endotracheal intubation and mechanical ventilation, high-flow oxygen (>20 L/min with $\text{FIO}_2 \geq 50\%$), noninvasive positive pressure ventilation, extracorporeal membrane oxygenationAny AE entry of: respiratory failure, shock, multisystem organ failure/dysfunction, ARDS, or acute lung injury
Severe COVID-19, as defined in Section 2.2.2 of the protocol	Positive local RT-PCR test at baseline, none of the criteria for critical COVID-19, and one of the following: 
Any of the following signs/symptoms: shortness of breath at rest, $\text{RR} \geq 30$ breaths per minute, $\text{HR} \geq 125$ beats per minute, $\text{SpO}_2 \leq 93\%$.Concomitant procedure of oxygen therapyCOVID-19 related MAV hospitalization (≥ 24 hours) or ICU admission.
Moderate COVID-19, as defined in Section 2.2.2 of the protocol	Positive local RT-PCR test at baseline, none of the criteria for severe or critical COVID-19, and any of the following signs/symptoms: shortness of breath with exertion worse than usual, $\text{RR} \geq 20$ and < 30 breaths per minute, heart rate ≥ 90 and < 125 beats per minute
Mild COVID-19, as defined in Section 2.2.2 of the protocol	Positive local RT-PCR test at baseline, none of the criteria for moderate, severe, or critical COVID-19, and any of the following symptoms: fever, chills, cough, sore throat, congestion, muscle or body aches, fatigue, headache, nausea, loss of taste or smell, vomiting, diarrhea.

SARS-CoV-2 test: The number and percentage of participants with a local SARS-CoV-2 test performed, and for those with a test performed, the specimen type, assay type, and result will be presented. The duration from the local positive SARS-CoV-2 test (defined as the time from date of the test performed to the date of randomization) will be summarized with descriptive statistics and summarized categorically (0 days, 1-2 days, 3-5 days, >5 days). Baseline SARS-CoV-2 RT-qPCR results from the sample collected by NP swab and from the saliva sample will be presented as will descriptive statistics of the baseline viral load (\log_{10} copies/mL) from each sample type. Baseline qualitative serology (SARS-CoV-2 antibody) status will be summarized based on qualitative serology assay (positive, negative). Baseline overall serology status based on three serology assays (qualitative, IgA, and IgG) will be summarized (positive if at least one serology assay is positive, missing if all three assays are missing, negative otherwise). Results of the baseline MNT test assay (not detected, detected) will be summarized.

Respiratory pathogen test: The presence of additional pathogens on Day 1 from the respiratory pathogen panel assay will be summarized.

SARS-CoV-2 variant: The number and percentage of participants with baseline isolates by PANGO lineage and CDC classification as variant of concern, variant of interest, variant being monitored, or other variants identified ([CDC 2021](#)) will be summarized in the FAS based on SARS-CoV-2 sequencing data. If baseline sequencing data are missing, available post-baseline sequencing data may be used. Participants without sequencing data will be summarized by suspected non-Omicron or Omicron variant (see Section [4.5.3](#)).

Participant clinical characteristics will be presented in a listing.

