2.2.2. COVID-19 Severity Categorization

The following COVID-19 severity categorizations are adapted from the FDA COVID-19 Developing Drugs and Biological Products for Prevention or treatment Guidance for Industry ([FDA 2021b](#)). Only participants with mild and moderate disease severity are eligible for study participation. Progression to severe or critical disease will be evaluated as a secondary endpoint.

Mild COVID-19 is defined as having a positive test by standard RT-PCR assay or equivalent test plus the following:

- Symptoms of mild illness with COVID-19 that could include fever, cough, sore throat, malaise, headache, muscle pain, or gastrointestinal symptoms, **without shortness of breath or dyspnea.**

- Respiratory rate <20 breaths per minute and heart rate <90 beats per minute.
- No clinical signs indicative of moderate, severe, or critical illness severity.

Moderate COVID-19 is defined as having a positive test by standard RT-PCR assay or equivalent test plus the following:

- Symptoms of moderate illness with COVID-19, which could include any symptom of mild illness or **shortness of breath with exertion worse than usual**.
- Clinical signs suggestive of moderate illness with COVID-19, such as respiratory rate ≥ 20 breaths per minute, with $\text{SpO}_2 > 93\%$ on room air at sea level, or heart rate ≥ 90 beats per minute.
- No clinical signs indicative of severe or critical illness severity.

Severe COVID-19 is defined as having a positive test by standard RT-PCR assay or equivalent test plus the following:

- Symptoms suggestive of severe systemic illness with COVID-19, which could include any symptom of moderate illness or **shortness of breath at rest**, or respiratory distress including the need for initiation of oxygen therapy.
- Clinical signs suggestive of severe systemic illness with COVID-19, such as respiratory rate ≥ 30 breaths per minute, heart rate ≥ 125 beats per minute, $\text{SpO}_2 \leq 93\%$ on room air at sea level or ratio of arterial oxygen partial pressure to fractional inspired oxygen ($\text{PaO}_2/\text{FiO}_2$) < 300 mm Hg.
- No criteria for critical severity.

Critical COVID-19 is defined as having a positive test by standard RT-PCR assay or equivalent test plus the following:

- Evidence of critical illness, defined by at least one of the following:
 - Respiratory failure based on resource utilization requiring at least one of the following:

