4.1.1. Inclusion Criteria

Each participant must meet all of the following criteria to be enrolled in this study:

1. Age: Is an adult aged 18 years and above, or is an adolescent aged 12 to 17 years (inclusive) and weighing ≥ 40 kg at the time of screening

Note: Adolescent enrollment will open only upon sponsor communication to sites after iDMC review of safety data in adults, and only if permitted by the local health authority.

2. Has had a SARS-CoV-2 positive antigen test, or by RT-PCR, or other locally approved molecular diagnostic assay obtained within 5 days prior to randomization.

Note: A historical record of a positive result from a test conducted within 5 days prior to randomization is acceptable. SARS-CoV-2 antibody testing cannot be used for study eligibility.

3. Has had initial onset of one or more of the following self-reported COVID-19-related signs or symptoms within 5 days prior to randomization:

- measured temperature ≥ 38 °C (100.4 °F)
- subjective fever (feeling hot or feverish)
- chills (shivering)
- cough
- sore throat
- congestion (stuffy or runny nose)
- shortness of breath or difficulty breathing with exertion worse than usual
- muscle or body aches
- fatigue (low energy or tiredness)
- headache

- k. loss of taste or smell
- l. nausea or vomiting
- m. diarrhea

4. Has mild or moderate COVID-19 (per Section 2.2.2) with one or more of the following COVID-19-related signs or symptoms on the day of randomization:

- a. measured temperature ≥ 38 °C (100.4 °F)
- b. subjective fever (feeling hot or feverish)
- c. chills (shivering)
- d. cough
- e. sore throat
- f. congestion (stuffy or runny nose)
- g. shortness of breath or difficulty breathing with exertion worse than usual
- h. muscle or body aches
- i. fatigue (low energy or tiredness)
- j. headache
- k. loss of taste or smell
- l. nausea or vomiting
- m. diarrhea

5. Is at high risk of disease progression defined as:

- a. Age ≥ 55 years
- b. Age 18 to <55 years with one or more preexisting medical conditions as follows
 - i. Obesity (body mass index [BMI] ≥ 30 kg/m²)
 - ii. Diabetes (Type 1 or Type 2)
 - iii. Chronic kidney disease (eGFR calculated by Modification of Diet in Renal Disease [MDRD] of 59 mL/min/1.73 m² or less, including end-stage renal disease on hemodialysis)
 - iv. Chronic lung disease (emphysema/chronic obstructive pulmonary disease, chronic bronchitis, interstitial lung disease [including idiopathic pulmonary fibrosis], or cystic fibrosis)

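### SAP Table 3 gives no programmatic severity grade to participants without a positive local RT-PCR, although entry accepts other tests

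*SAP*

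**What the plan says.** Each row of Table 3 (SAP 5.2.2) names a grade, refers it to protocol section 2.2.2 and gives a rule:

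- Critical: "Positive local RT-PCR test at baseline, and one of the following".
- Severe: "Positive local RT-PCR test at baseline, none of the criteria for critical COVID-19, and one of the following".
- Moderate: "Positive local RT-PCR test at baseline, none of the criteria for severe or critical COVID-19, and any of the following signs/symptoms".
- Mild: "Positive local RT-PCR test at baseline, none of the criteria for moderate, severe, or critical COVID-19, and any of the following symptoms".

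There is no fifth row and no fallback. On when the rule is applied, the SAP says: "The programmatic derived COVID-19 severity will be performed at baseline and for the maximum severity through Day 29". SAP 5.2 presents these summaries in the FAS, the mFAS-non-Omicron and the mFAS-Omicron.

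Protocol 2.2.2 defines every grade as "having a positive test by standard RT-PCR assay or equivalent test" plus clinical criteria. SAP 3.5.1 keeps that alternative for severe and critical disease.

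For entry, inclusion criterion 2 reads: "Has had a SARS-CoV-2 positive antigen test, or by RT-PCR, or other locally approved molecular diagnostic assay obtained within 5 days prior to randomization". Footnote d of the schedule of assessments says the same. Germany is the exception: protocol 12.5.1 requires RT-PCR there, with room to add methods if the national testing strategy changes.

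SAP section 1 says the SAP governs where its methods differ from the protocol's. SAP section 7 declares no changes from the protocol.

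**The concern.** Table 3 is a programming rule, and its test condition is narrower than both the entry criterion and the definition it is meant to implement. A participant can be properly enrolled on an antigen result, be intubated for COVID-19, and fit no row. Because the SAP takes precedence over the protocol, the protocol's wider wording does not rescue the derivation. Because SAP section 7 declares no changes, the narrowing does not look deliberate.

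At stake are the completeness and level of the programmatic severity tables at baseline and as the Day 29 maximum.

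**Working it through.** The plan gives no figure to reproduce here, so the check is of the logic, followed by an illustration of size.

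**1. Can another planned test meet the condition?** The schedule requires one positive local test of any accepted type. The Day 1 RT-qPCR on nasopharyngeal swab and saliva is listed under central laboratory assessments, so it is not a local test. Nothing obliges a site to add a local RT-PCR. Footnote d allows extra local testing for case management, so some antigen-enrolled participants may have one.

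**2. What does the rule return?** Take four yes/no inputs: whether the critical, severe, moderate and mild clinical criteria are met. That gives 2^4 = 16 combinations, graded at the highest level met.

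| Local RT-PCR | Critical | Severe | Moderate | Mild | No grade |
|---|---|---|---|---|---|
| Positive | 8 | 4 | 2 | 1 | 1 |
| Not positive | 0 | 0 | 0 | 0 | 16 |

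With a positive local RT-PCR, only the combination with no criteria met goes ungraded. Without one, every combination does, including mechanical ventilation (a critical criterion) and a COVID-19-related hospitalization of at least 24 hours (a severe criterion).

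**3. Direction of the error.** Ungraded participants can be missing from the severe and critical rows but cannot be added to them. Under SAP 4.1 the default denominator is everyone in the treatment group within the analysis set. Ungraded participants therefore stay in the denominator and lower the percentages as well.

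**4. Conflict within the SAP.** SAP 3.5.1 imputes severe/critical COVID-19 for anyone who meets the primary endpoint. An antigen-only participant hospitalized for COVID-19 through Day 29 would count as severe/critical in the first key secondary endpoint and have no grade in the programmatic table.

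**5. Size.** Let s be the share with no positive local RT-PCR on record. The number ungraded is s × N, with N = 399 randomized and about 320 in the mFAS-non-Omicron (SAP 4.2). The documents do not give s; the values below are assumptions.

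| Assumed s | s × 399 | s × 320 |
|---|---|---|
| 10% | 39.9, about 40 | 32 |
| 25% | 99.75, about 100 | 80 |
| 50% | 199.5, about 200 | 160 |

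**The case against.** The strongest reply is that nothing inferential depends on Table 3. That stands. The first key secondary endpoint uses the investigator's assessment on the eCRF (SAP 3.5.1), with severe/critical imputed for primary-endpoint events. SAP 5.5.3 also imputes severe/critical when a visit's assessment is missing while the participant is in hospital for COVID-19. The sensitivity analyses in SAP 5.5.3.1 are multiple imputation and a repeat in the per-protocol set. A reader might infer that the programmatic grade is the objective check on the investigator's grading for that endpoint, but no section gives it that role. Table 3 sits among the descriptive clinical characteristics.

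Three other stronger readings also go too far:

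- *Every antigen-enrolled participant loses a grade.* Anyone who also has a positive local RT-PCR on record is graded.
- *Severe and critical counts fall in proportion to the share ungraded.* That assumes test type is unrelated to outcome, and the documents give no basis for it.
- *The treatment comparison is biased.* The qualifying test precedes randomization, which is 1:1 and stratified by country, so no difference between arms is shown.

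It can also be said that the loss would be visible, since assay type is tabulated (SAP 5.2.2) and count tables carry a row for missing values as needed (SAP 4.1). That would show the gap but not close it. Nor can programmers be relied on to read the condition generously when the SAP wording takes precedence.

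**Conclusion.** Wrong as written, and minor. The mismatch between Table 3, inclusion criterion 2 and protocol 2.2.2 is plain on the text. Its certain consequence is that participants without a positive local RT-PCR on record get no programmatic grade at either time point. The programmatic summaries in all three analysis sets would be incomplete and would understate severe and critical disease wherever such a participant met those criteria.

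The extent rests wholly on the unknown share s. Sites in Germany would be spared while RT-PCR remained the only accepted entry test there.

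The primary and key secondary analyses are unaffected. The mild/moderate subgroup in SAP 5.6 would be affected only if it uses the programmatic grade, and the SAP does not say which severity source it uses.

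**What to change.** In all four rows of Table 3, replace the test condition with: *Positive local SARS-CoV-2 test at baseline (antigen, RT-PCR or other locally approved molecular assay, as accepted under inclusion criterion 2)*. Naming the tests also settles what counts as equivalent, which protocol 2.2.2 leaves undefined. Every participant who meets criterion 2 then passes the test condition and is graded on the clinical criteria.

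The cost is one wording change and one programming condition, to be made before the unblinding that follows the Day 29 soft lock. No new data are needed: protocol 6.1 already has the local result and assay type recorded in the eCRF. If a PCR-confirmed view is wanted, the mFAS-PCR sets in SAP 4.5.4 provide one.
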